During this prospective randomized controlled trial, we will include all patients contacting the OHGPS via 112 or 1733 over the phone who are subsequently visited by physicians from OHGPS in Belgium. If recruitment is slower than anticipated, a second OHGPS will be recruited.

Whenever a patient requires medical help, his family or a bystander can call the 112 emergency number or, if a GP is needed, the 1733 number (Figure 1).

The urgent calls received by the OHGPS phone operator are transferred to the GP on duty. For the other calls, the patient is invited to go to the OHGPS. For home visits, GPs have a dedicated car with a chauffeur at their disposal, to avoid parking problems and to have additional support available (Figure 1).

For each home visit, GPs on duty register all visits, urgent and not urgent, as they usual do. Because they have to write a report to the patient's GP, presenting complaint(s) and diagnosis are recorded for every home visit.

Before the study, all GPs and chauffeurs are informed about the study design and the detailed procedures, and have to sign the informed consent form (ICF) respectively for GPs and chauffeurs. The main researcher developed an extensive training video showing how to use the PICO™ monitor. All GPs and chauffeurs of the OHGPS have access to this video at any time and will receive a written manual.

Each patient seen at home is considered as having requested an urgent visit and, consequently, is eligible to enter the study. Before entering the residence, each patient will be allocated to one of two arms, according to the results of the randomisation process [16] (see the procedure in the statistics section). The first arm is the intervention arm where the monitoring device (figure 2) is used, additional to usual care, and the second arm is usual care only, without the use of the monitoring device.

[figure not shown]

Figure 1: flowchart of calls arriving at the emergency dispatch centre in the region of Leuven, Belgium

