* Total number: total number of patients for whom a home visit was requested during the registration period.

** Other reasons: when the GP on-call deems the intervention as not urgent, ICF withdrawn after previous acceptance,

*** Distribution of patients: number of patients cared for onsite in the OHGPS and number of patients for whom a home visit is requested.

Exclusion criteria

Patients younger than 18 years of age, not seen during home visits, failed to provide informed consent, with an acute trauma but not in a possible life-threatening situation (e.g. a broken bone), found lying on the street or seen after the intervention of an ambulance, a PIT or a MET (because in such situation monitoring devices are already on scene before arrival of a GP).

Reasons for exclusion will be recorded (not meeting inclusion criteria, refusing to participate, other reasons): these patients will not be included in the study.

Statistics

Randomisation

The cases are randomly assigned to two arms on a 1:1 ratio (via random number generator on “<http://www.random.org>” [16]): 1 group with and 1 group without the use of the monitoring device PICO™. Randomization will be stratified at the OHGPS level and by GP’s intervention vehicle and will be randomised in blocks of 6.

Sample size

The OHGPS is open on weekends, from Friday 19:00 h until Monday 08:00 h, and the service responds to an average of 54 calls for urgent home visits per week-end. Based on prevalence of emergency

diagnoses in the Intego data [19], I calculated that 10% of the calls are very urgent and 25% require an urgent decision but are not always followed by a hospitalisation. The presumption is that GPs generally refer 21% of the patients inappropriately to hospital or to patient's own GP. To achieve a minimal clinically significant difference of 11% more patients receiving an appropriate decision regarding referral to hospital or not in the intervention group compared to the control group, one will need 866 patients, 433 patients in each arm.

To yield minimally 866 included patients during urgent home visits, the estimation that the study will last for minimum 6 months is based on the consideration that an average of 25% of patients will not provide informed consent.

Data recorded

The aim is to record

- the number of calls at the 112 dispatch centre by means of the 112 or 1733 dial number and the 112's decision.
- the number of calls dispatched from 112 to the OHGPS phone operator.

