To explain how to use and apply the PICO™, a written manual and an extensive video have already been prepared. Each participant will receive a written copy and access to the training video at all time.

Since in case of urgency GPs must be able to focus on the patient, we decided that the chauffeur would accompany the GP to the patient and connect the device if asked to do so according to the randomization process. One of the reasons is that the turn-over of the chauffeurs is lower than of the GPs on call, which means that the risk of errors due to incorrect application or protocol violations will also be lower.

Urgent home visits

Each time a patient asks a doctor for a home visit during out-of-hours periods, it is considered as an urgent call. For a non-urgent problem, the patient is considered to be able to visit the OHGPS, where a physician can be consulted. Therefore, it was considered feasible to perform randomisation before the patient was seen.

Randomisation

For this randomised control trial, the number of cases needed is first calculated. Each case is allocated to the result of the randomisation. The monitoring device will be installed accordingly. It was decided to stratify at the OHGPS level and by the intervention vehicle. For each vehicle, the block randomisation will be applied in blocks of six. Each intervention form will be used according to the assigned rank number for which an envelope with the result of the randomization is provided. Block randomisation

was chosen because sometimes two vehicles and GPs are on the road at the same time and home visits can therefore be executed simultaneously.

Consequently, at the start and certainly before the GP leaves the vehicle, the randomisation envelope will be opened to know if for that specific home visit the monitoring device will be used. If the decision is to apply the monitoring device, the chauffeur has to accompany the GP. In the other situation, he will not and the GP will provide care as per usual.

In the intervention arm, the monitoring device will be applied, with one pulse oximeter device on a finger and five electrodes on the bare chest of the patient for an ECG. If needed, the GP can also apply the thermometer. When another investigation is done simultaneously, e.g. a full ECG record by another device, this will be considered as usual care and mentioned in the intervention form.

Informed consent form and patient's agreement

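### One fixed block size of six per vehicle in an unmasked trial makes up to a quarter of allocations foreseeable, and the planned records could not show selection by foreseen arm

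*Combined protocol and SAP*

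**What the plan says.** Statistics, Randomisation: "The cases are randomly assigned to two arms on a 1:1 ratio", and "Randomization will be stratified at the OHGPS level and by GP’s intervention vehicle", and the cases "will be randomised in blocks of 6". The Discussion (Randomisation) repeats it: "For each vehicle, the block randomisation will be applied in blocks of six". No variation in block size is mentioned. The reason given for blocking is that two vehicles may be out at the same time.

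The mechanism is an envelope per form: "Each intervention form will be used according to the assigned rank number for which an envelope with the result of the randomization is provided". As to timing, "at the start and certainly before the GP leaves the vehicle, the randomisation envelope will be opened". The result is then plain to the crew: "If the decision is to apply the monitoring device, the chauffeur has to accompany the GP"; otherwise the GP goes in alone.

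Method, Study Design says that before the study "all GPs and chauffeurs are informed about the study design and the detailed procedures". The Discussion adds that chauffeurs turn over less than the GPs on call.

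The plan does keep records of visits. Study Design has GPs register every home visit, urgent or not. The exclusion criteria require reasons for exclusion to be recorded. Table 1 counts all requested home visits, with excluded and included columns. Its footnote accepts the GP's view that a visit was not urgent as an exclusion reason, although Study Design treats every patient seen at home as an urgent request and eligible.

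**The concern.** With one fixed block size, anyone who sees past allocations and knows the size can count. Here each vehicle has its own short sequence and the crew sees every allocation in it. Towards the end of a block the next arm is often known, and otherwise it can be guessed at better than even odds, before the envelope is touched.

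That opens a decision point ahead of randomisation: whether to open an envelope for this visit at all, with the arm already foreseen. The motive is plausible, since the Discussion itself describes the device as an extra burden on GPs. If visits expected to be busier, sicker or easier were passed over more often when one arm was due, the arms would differ for reasons other than the device. The planned records could not reveal this, because a visit skipped before opening has no allocation.

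**Working it through.** The documents give no figure for predictability, so there is none to reproduce.

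**Inputs.** Ratio 1:1 and block size six (Statistics, Randomisation), hence three device and three usual-care visits per block; 866 included patients and 25% non-consent (Sample size). The 25% non-consent and the 25% derived below are unrelated quantities.

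**Certainty.** A block has C(6,3) = 20 equally likely orderings. The next arm is certain once one arm is used up.
- Position 4: the first three share an arm, 2/20 = 1/10.
- Position 5: the last two share an arm, 8/20 = 2/5.
- Position 6: always.

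**Best guess.** The strategy is to name the arm with more places left.

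| Position | Next arm certain | Best guess correct |
|---|---|---|
| 1 | 0 | 1/2 = 0.5 |
| 2 | 0 | 3/5 = 0.6 |
| 3 | 0 | 2/5 × 3/4 + 3/5 × 1/2 = 0.6 |
| 4 | 1/10 | 1/10 × 1 + 9/10 × 2/3 = 0.7 |
| 5 | 2/5 | 2/5 × 1 + 3/5 × 1/2 = 0.7 |
| 6 | 1 | 1 |
| Sum | 1.5 | 4.1 |

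Share certain: 1.5/6 = 25%. Share guessed correctly: 4.1/6 = 68.3%, against 50% by chance.

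**Counts.** On included patients, 0.25 × 866 = 216.5, about 217. Envelopes are opened before consent, so the sequence runs over more visits: 866/0.75 ≈ 1155 envelopes, and 0.25 × 1155 ≈ 289.

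**Cost of dropping blocks.** Under unrestricted 1:1 allocation the difference D between arm sizes has SD √866 = 29.4. Efficiency relative to equal arms is 1 − (D/866)², with expectation 1 − 1/866 = 0.9988, a loss of about 0.1%. Even at D = 1.96 × 29.4 ≈ 58 the loss is only (58/866)² ≈ 0.4%.

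**Varied block sizes.** Simulation of 100,000 allocations, for a crew that knows the mix of sizes but not the size of the current block (the mixes are assumptions):

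| Sizes | Certain | Best guess correct |
|---|---|---|
| Fixed 6 | 25% | 68% |
| 4, 6 | 5% | 69% |
| 4, 6, 8 | 2% | 68% |
| 4, 8, 12 | 3% | 66% |

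Varying the size removes most of the certainty but little of the guessing advantage.

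**The case against.** **A skipped visit might be thought to leave no trace.** A reader could infer this, but the documents do not support it. All home visits are registered, exclusion reasons are recorded, and Table 1 counts every requested visit. A visit passed over should therefore appear as a registered visit with an exclusion reason and no numbered form. What remains is narrower: that trace carries no arm and no stated link to an envelope number, and not urgent is an accepted reason.

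**A reader might infer that crews will know a quarter of allocations.** That is an upper bound. It needs someone who knows the block size, knows where the block began and has followed the vehicle since. The documents say that crews are briefed on design and procedures, not that the block size is disclosed. Chauffeur turnover is described only as lower than that of GPs. By the same sentence, the GP, who judges urgency and takes consent, is the less well placed to follow the sequence.

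**A reader might infer that crews could steer calls between two cars.** Nothing in the documents gives them that choice. Urgent calls are transferred by the phone operator to the GP on duty.

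**The added harm is smaller than it looks.** Before opening, the crew has only the call information. After opening, the arm is known for every visit, the patient is then seen, and a quarter are expected not to consent, while only consenting patients are analysed. Anyone wishing to select needs no counting. This stands, and it limits the weight of the point. It does not remove the point: if opening were moved to after consent, fixed blocks would still let the arm be foreseen and would undercut that repair.

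**Conclusion.** The concern holds as a foreseeable and avoidable weakness, worth correcting before the first patient. The single block size, the separate sequence per vehicle and the visibility of past allocations are all stated, and the arithmetic is exact: up to 25% of allocations certain and 68% guessable. How much of that is realised depends on two things the documents leave open: whether the block size reaches the crew, and whether anyone follows the sequence. The briefing and the lower chauffeur turnover make both plausible.

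No size of bias can be given, and none is claimed. From the records as described, selection by foreseen arm could be neither shown nor ruled out. Blocking returns almost nothing at this sample size, and its stated reason is already met by giving each vehicle its own list. The disclosure of the arm before consent is the larger problem and needs its own remedy.

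**What to change.** Before the first patient:

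1. Generate a separate unrestricted 1:1 list for each vehicle and new numbered envelopes from it. This removes predictability altogether. The separate lists then serve logistics only, so the wording on stratification and blocks should be changed to match.
2. If blocks are kept, use sizes that vary at random, include sizes above six, and withhold them from GPs and chauffeurs. This is second best, since about 2–5% of allocations stay certain for a crew that knows the mix (in the sizes tried) and guessing stays near 66–69%.
3. Under either option, leave the block scheme out of the GP and chauffeur briefing. The protocol says those meetings had not yet taken place when it was written.
4. Reconcile every registered home visit with an envelope number. Report visits for which no envelope was opened and, by arm, opened envelopes that did not lead to inclusion. If vehicle and time are logged, visits without an envelope can also be tabulated by the arm of the next envelope opened in that vehicle, which is the arm they would have received.
5. Reconcile the Table 1 footnote on non-urgent visits with the Study Design statement that every home visit is eligible.

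The cost is a new list and envelopes, a short protocol change and a simple log. Under option 1 the arms will not be exactly 433 and 433; they may differ by a few tens, at about 0.1% expected loss of efficiency. The planned two-sample z-test needs no change.

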- the decision of the OHGPS phone operator.
- all data on the intervention form for both study arms, for each patient, who gave IC. These data consist of those filled in by the GP on-call immediately after the intervention (Table 2)
 - o first (when deciding on referral) and final (when completing the intervention form) diagnostic hypothesis;
 - o referral to hospital or not;
 - o parameters and curves inspected and results;
 - o if any alarm was given and noticed;
 - o the impact of the device parameters on the decision;
 - o if the device brought new elements;
 - o the feeling of the GP about the improvement or not by the device in communication with the healthcare professional;
 - o which parameters helped the communication and if they were showed or viewed by the EP.
- After 30 days
 - o the information provided by the patient's own regular GP, regarding the patient's outcome;
 - o the information concerning the diagnosis at arrival at the ED and, if available, the outcome of the patient until day 30 of the hospital admission.

Analysis

I will compare the amount of (verified or experienced) emergencies with the non-urgent home visits, the number of patients correctly referred to hospital or not. The difference in proportions in both groups will be tested by the Z-test. I will also test for the difference in proportions in the groups using the monitoring device and the usual care group, with the z-statistic for two-sample test of proportions reporting the z-test statistic and the associated *p*-values. All *p*-values smaller than 0.05 will be considered statistically significant. The statistical analyses will be performed with R software version 3.5.1 [20].

The definition of an incorrect referral is stated as follows:

- When a patient is referred to hospital and released within 12 hours. However, if the referral is made only for a diagnostic test, e.g. an X-Ray, an ECG, a blood test, advice of a consultant .., and no hospitalisation followed, it is considered as a correct referral.
- If a patient is referred to hospital only for a diagnostic test (e.g. X-Ray) and no hospitalisation is requested, but an in-hospital decision is made to hospitalise the patient.
- If a patient is referred to his own GP but needs a hospitalisation within 48 hours.

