The alarms are produced by the device when a wire is not registering or is disconnected, when the battery is low, when apnoea or asystole is present, or when the value is out of the set limits for each parameter. Therefore, alarms will be enabled on each device and the upper and lower limits will be set on each device. I will use the device's pre-installed lower limits: for SpO₂ ≤92%, for respiration rate (RR) at ≤10 respirations per minute and the upper limits for temperature at ≥39°C and for HR at ≥120 beats per minute (bpm). I will change the automatically set lower limits for pulse rate and HR at ≤50 bpm instead of 30 bpm and the upper limit for RR to ≥30 respirations per minute.

Referral

The data produced by the device could help the GP to follow the evolution of the disease and to establish his tentative diagnosis. Deciding about the treatment and referral of the patient to hospital or to their own GP, is the responsibility of the GP and is based on his usual approach of the situation.

It was needed to decide what a correct referral is. A referral to the patient's own GP is considered incorrect if the patient cannot be treated at home up to 48 hours after the initial urgent visit and has to be admitted to hospital. It is however considered as correct if the patient needs to be hospitalised for another reason than the reason of the home visit. In exceptional cases, the patient could request a new urgent visit during the same out-of-hours period. The visiting GP will include the patient if the informed consent is obtained and follow the study procedure, but will record that the patient was seen less than 48 hours before. The first home visit referral is consequently considered as incorrect. It is also possible that a patient is transported by ambulance or MET within 48 hours of the GP on-call visit: the referral will then be considered as incorrect if the patient was initially sent home, based on the records obtained from the patient's own regular GP, 30 days after the first intervention.

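### The repeat-visit rule scores a first decision incorrect without any admission, which contradicts the plan's own 48-hour hospitalisation criterion for patients left at home

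*Combined protocol and SAP*

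**What the plan says.** The main comparison is the proportion of patients correctly referred, or correctly not referred, to hospital. The plan defines an incorrect decision in two places.

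- **Analysis section.** Three situations are listed as incorrect. The only one for a patient not sent to hospital is: "If a patient is referred to his own GP but needs a hospitalisation within 48 hours". A repeat visit is not on the list.
- **Discussion, Referral.** This text opens with the same idea: leaving the patient to their own GP is incorrect if home treatment fails within 48 hours and admission follows. It then exempts an admission for a reason other than that of the home visit. Next comes a further rule: "In exceptional cases, the patient could request a new urgent visit during the same out-of-hours period". At that second visit, "The visiting GP will include the patient if the informed consent is obtained and follow the study procedure", and the GP "will record that the patient was seen less than 48 hours before". The consequence is: "The first home visit referral is consequently considered as incorrect".

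The Sample size section gives the opening hours of the service: "The OHGPS is open on weekends, from Friday 19:00 h until Monday 08:00 h". The Discussion (Randomisation) describes a finger probe and five chest electrodes in the device arm. The consent text says that the patient is told when the device is to be fitted. No masking of patients is described.

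**The concern.** The endpoint is meant to judge whether hospital was the right destination. For a patient left at home, the Analysis section judges this by a hospital event. The repeat-visit rule replaces that event with a request for a second visit and does not look at what the visit found. Two analysts following different sections could score the same record differently on the main endpoint.

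The trigger is also open to influence by allocation. The patient knows whether a monitor was attached and decides whether to ask for help again. Being monitored might reassure some patients and worry others. Either way, repeat visits could differ between arms while the GPs' referral decisions did not. The direction cannot be predicted from the documents.

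**Working it through.** **1. The two definitions applied to one patient.** Take a patient left at home, seen again in the same weekend, left at home again, and never admitted.

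| | Visit 1 | Visit 2 |
|---|---|---|
| Analysis section (hospitalisation within 48 h) | correct | correct |
| Referral, repeat-visit rule | incorrect | correct |

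The same decision in the same patient gets opposite scores at visit 1. No event rate is needed to show this.

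**2. Reason for the second visit.** The other-reason exemption is written for hospitalisation and comes before the repeat-visit rule. The text does not say whether it extends to a repeat visit for a new problem.

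**3. Time window.** Friday 19:00 to Monday 08:00 is 5 + 24 + 24 + 8 = 61 h. A repeat visit 48 to 61 h after the first can lie in the same out-of-hours period, yet it is outside the under-48-hour note that the GP makes. Whether the rule covers it is unclear.

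**4. Possible size.** The documents give no repeat-visit rate, so the following inputs are assumptions: 2% to 4% of visits lead to a repeat visit, and half of these end without an admission for the same problem.

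- Mis-scored share: 0.5 × 2% = 1%, up to 0.5 × 4% = 2%.
- Per arm of 433: 433 × 0.01 = 4.3, up to 433 × 0.02 = 8.7 patients.
- If such visits were half as common in one arm: 1% − 0.5% = 0.5 point, up to 2% − 1% = 1 point of false difference.

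**5. Effect on the test.** From the plan: 433 per arm, 21% inappropriate decisions in the control group, a two-sample z-test at 0.05 (taken as two-sided, which is not stated). Assume no true difference, so 21% in both arms before mis-scoring. With scored rates a and b, d = a − b and mean rate m:

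SE0 = √[2m(1−m)/433]; SE1 = √{[a(1−a) + b(1−b)]/433}

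rejection = Φ[(d − 1.96·SE0)/SE1] + Φ[(−d − 1.96·SE0)/SE1]

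| Added to arm a | Added to arm b | Scored incorrect | Rejection |
|---|---|---|---|
| 1 point | 1 point | 22% v 22% | 5.0% |
| 1 point | 0.5 point | 22% v 21.5% | 5.4% |
| 2 points | 1 point | 23% v 22% | 6.4% |

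Equal rates do not inflate false positives. Unequal rates do so slightly.

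**6. Effect on an observed result.** At the planned effect (read as 21% v 10%), the counts are 0.21 × 433 ≈ 91 and 0.10 × 433 ≈ 43. Removing 9 and 4 mis-scored patients gives 82 v 39, z = 4.2, p < 0.0001, so the conclusion stands. A borderline result behaves differently: 95 v 72 gives z = 1.98, p = 0.048.

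- Removing 5 from each arm (90 v 67): p = 0.042, still significant.
- Removing 4 and 2 (91 v 70), the assumed two-to-one imbalance: p = 0.067.

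**The case against.** The strongest defence is that an urgent return visit is a prespecified marker of failed home management, and that preferring admission alone is partly taste. That would carry weight if the plan used the marker consistently. It does not, because the Analysis section lists what counts as incorrect and omits it. The plan also has at least two researchers review all information, but gives them no criterion for setting the repeat-visit score aside.

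Other parts of the defence stand and limit the point:

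- **Visits, not calls.** A reader might infer that any further call makes the first decision incorrect. The rule concerns a new visit at which the study procedure is followed. A call handled without a visit is not addressed.
- **48 to 61 hours.** A reader might infer that a repeat visit at 50 to 60 h certainly counts as failure while an admission at that hour does not. The GP's note that the patient was seen under 48 hours earlier suggests that the rule may share the 48-hour limit. This is an ambiguity, not a proven conflict.
- **Patients sent to hospital.** A reader might infer that a patient kept in hospital beyond 12 hours who asks for a visit later that weekend becomes incorrect. The surrounding text is about patients sent to their own GP, and hospital referrals have their own paragraph, so this reading is strained.
- **Flipped significance.** Removing 5 repeat visits from only one arm takes 95 v 72 to 90 v 72 and p = 0.12. That one-sided removal is selective and does not represent the likely effect.

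**Conclusion.** The plan contains two incompatible scoring rules for a first visit that left the patient at home, and they need reconciling before any outcome is classified. This rests on the text alone.

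The risk of bias is plausible but small. It depends on assumed repeat-visit rates, on an assumed difference between arms, and on the well-supported inference that patients know whether they were monitored. A difference of 0.5 to 1 point is minor beside the planned 11% and would matter only for a borderline result. The documents do not support saying that the endpoint has become a count of call-backs, or that the bias favours either arm. The change is still worth making, because the rule can give a contradictory score on the main endpoint and is cheap to correct.

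**What to change.** Reconcile the Analysis section with the Referral text by deleting the automatic repeat-visit rule, and state the following in both places:

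- For a first visit that left the patient at home, apply the existing Analysis criterion. The decision is incorrect if hospitalisation follows within 48 hours of that first visit, including one arranged at the repeat visit. The existing other-reason exemption applies.
- The rules for patients referred to hospital, including the 12-hour rule, stay as they are. Without this limit, the new wording could turn a patient released within 12 hours from incorrect to correct.
- Report the number of repeat visits by arm as a separate descriptive count.

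This also settles the 48 to 61 h question, since a repeat visit alone no longer affects the score. The cost is about one sentence of wording. The plan already collects admission data from the regular GP and the hospital, and the sample size does not change. The downside is that a few first visits move from incorrect to correct.
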